### 1.3 List of Abbreviations and Definition of Terms

#### Abbreviations

$\alpha$ -CCP Ab	Anti-Cyclic Citrullinated Antibody
ACR	American College of Rheumatology
AE	Adverse Event
ALT	Alanine Transaminase
AST	Aspartate Transaminase
ANC	Absolute Neutrophil Count
aPTT	Activated Partial Thromboplastin Time
AUC	Area under the plasma concentration-time curve
BID	Twice daily
BP	Blood pressure
BUN	Blood Urea Nitrogen
CBC	Complete Blood Count
CDAI	Clinical Disease Activity Index
CD4, CD8	Cluster Of Differentiation
CGC	Common Gamma-Chain
CHF	Congestive Heart Failure
CI	Confidence Interval
C max	Maximum Observed Plasma Concentration
COVID-19	Coronavirus Disease - 2019
CPK	Creatine Phosphokinase
CR	Clinical Remission
CRF	Case Report Form
CRP	C-Reactive Protein
CXR	Chest X-Ray
DAS	Disease Activity Score
DM	Diabetes Mellitus
DMARD	Disease-Modifying Anti-Rheumatic Drug
DNA	Deoxyribonucleic Acid
DTP	Direct-to-Patient
ECG	Electrocardiogram
eCRF	Electronic Case Report Form

EDC	Electronic Data Capture
EQ-5D	EuroQoL-5D
EULAR	European League against Rheumatism
eGFR	Estimated glomerular filtration rate
ET	Early termination
FACIT	Functional Assessment of Chronic Illness Therapy – Fatigue
FDA	US Food and Drug Administration
FPG	Fasting plasma glucose
FSH	Follicle Stimulating Hormone
GCP	Good Clinical Practice
GMCSF	Granulocyte macrophage colony-stimulating factor
gp130	Glycoprotein 130
HAQ-DI	Health Assessment Questionnaire – Disability Index
HDL	High Density Lipoprotein
hsCRP	High-Sensitivity C-Reactive Protein
HV	Healthy Volunteer
ICF	Informed Consent Form
ICH	International Conference on Harmonization
IEC	Independent Ethics Committee
IL	Interleukin
INR	International Normalized Ratio
IRB	Institutional Review Board
IRT	Interactive Response Technology
ITT	Intent-to-Treat
IVRS	Interactive Voice Response System
IWRS	Interactive Web Response System
JAK	Janus Activated Kinase
LDA	Low Disease Activity
LDL	Low Density Lipoprotein
MAD	Multiple Ascending Dose
MedDRA	Medical Dictionary for Regulatory Activities
MTX	Methotrexate
NK	Natural Killer Cells
NKT	Natural Killer T Cells

NCS	Non-Clinically Significant
NOAEL	No Observable Adverse Effect Level
NRI	Non Responder Imputation
NSAID	Non-Steroidal Anti-Inflammatory Drug
NYHA	New York Heart Association
OC	Observed Cases
OLE	Open-Label Extension
PE	Physical Examination
PG	Pharmacogenetic
PhGA	Physician's Global Assessment of Disease Activity on VAS
PK	Pharmacokinetic
PPD	Purified Protein Derivative

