## **5.0 Investigational Plan**

### **5.1 Overall Study Design and Plan: Description**

This is a Phase 2, multicenter, OLE study to assess the long-term safety, tolerability, and efficacy of upadacitinib in RA subjects who have completed Study M13-550 or Study M13-537 Phase 2 RCT with upadacitinib. This study is designed to enroll up to 500 subjects. Subjects will be treated for approximately 312 weeks.

Only those subjects who have met all of the specified inclusion criteria and none of the exclusion criteria will have an option to enter into the OLE study to receive upadacitinib, as long as the subject is willing and the Investigator believes that continuing therapy with upadacitinib is appropriate.

All eligible subjects will be assigned to upadacitinib 6 mg BID immediately after or up to 30 days following the Last Visit (Week 12) of Study M13-550 or Study M13-537 Phase 2 RCT.

Subjects who are unable to tolerate 6 mg BID will be discontinued from the study.

At Week 6, if a subject fails to achieve at least 20% improvement from RCT Baseline in both Tender Joint Count (TJC) and Swollen Joint Count (SJC), upadacitinib dose should be increased to 12 mg BID as long as the Investigator has no safety concerns. After 6 weeks of treatment with upadacitinib 12 mg BID, the improvement in TJC and SJC will be re-assessed at next scheduled visit (Week 12).

If the subject on 12 mg BID fails to achieve at least 20% improvement in both TJC and SJC from RCT Baseline the subject will be discontinued.

At Week 12, the same process will be followed. If a subject still on 6 mg BID fails to achieve at least 20% improvement from RCT Baseline in both TJC and SJC, upadacitinib dose should be increased to 12 mg BID. The improvement in both TJC and SJC will be re-assessed after 6 weeks of treatment with 12 mg BID at Week 18 (an optional study visit).

Subjects who fail to achieve at least 20% improvement from RCT Baseline in both TJC and SJC with 12 mg BID at Week 18 will be discontinued.

After Week 12, if a subject fails to show at least 20% improvement from RCT Baseline in both TJC and SJC at 2 consecutive scheduled study visits, the subject will be discontinued.

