### **5.4 Removal of Subjects from Therapy or Assessment**

#### **5.4.1 Discontinuation of Individual Subjects**

A subject may withdraw from the study at any time. The Investigator may discontinue any subject's participation for any reason, including an adverse event, safety concerns or failure to comply with the protocol.

Subjects will be withdrawn from the study immediately if any of the following occur:

- Clinically significant abnormal laboratory results or adverse events, which rule out continuation of the study medication, as determined by the Investigator and the AbbVie Therapeutic Area Medical Director.
- Serious infections (e.g., sepsis) which would put the subject at risk for continued participation in the trial as determined by the Investigator in consultation with the AbbVie Therapeutic Area Medical Director.
- The Investigator believes it is in the best interest of the subject.
- The subject requests withdrawal from study drug or the study.

- Inclusion and exclusion criteria violation was noted after the subject started study drug, when continuation of the study drug would place the subject at risk as determined by the AbbVie Therapeutic Area Medical Director.
- Introduction of prohibited medications or dosages when continuation of the study drug would place the subject at risk as determined by the AbbVie SDP.
- Subject is non-compliant with TB prophylaxis (if applicable) or develops active TB at any time during the study.
- The subject becomes pregnant while on study medication.
- Subject has known malignancy, except for localized non-melanoma skin cancer. Discontinuation for carcinoma in-situ of the cervix is at the discretion of the Investigator.
- Subject is diagnosed with lupus-like syndrome, multiple sclerosis or demyelinating disease (including myelitis).
- Subject is significantly non-compliant with study procedures which would put the subject at risk for continued participation as determined by the Investigator.
- Subject has failed to achieve at least 20% improvement from Baseline (RCT period) in TJC and SJC with upadacitinib as described in Section 5.1.
- Confirmed diagnosis of deep vein thrombosis, pulmonary embolus or non-cardiac, non-neurologic arterial thrombosis.
- Subject develops a gastrointestinal perforation (other than due to appendicitis or mechanical injury).

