### **5.6 Discussion and Justification of Study Design**

Subjects who have completed Study M13-550 or Study M13-537 RCT with upadacitinib will be allowed to enroll in the OLE study to continue to receive upadacitinib for up to approximately 312 weeks. The primary objective of OLE study is to collect long-term

safety and tolerability data for upadacitinib. All subjects who roll over into the OLE will be assigned to upadacitinib 6 mg BID initially, regardless of treatment assignment during RCT period, and the basis of this design is to preserve the blinding of treatment assignment in the RCT period. All subjects assigned to 6 mg BID initially will have an option to increase the dose to 12 mg BID (or 30 mg QD from January 2017) throughout the treatment period if a subject is unable to achieve low disease activity with upadacitinib 6 mg BID. At any time during the treatment period, the upadacitinib dose can be decreased back to 6 mg BID (or 15 mg QD from January 2017) per Investigator's judgment if there are safety and tolerability concerns. Those subjects who are unable to achieve at least 20% improvement in both SJC and TJC (minimum clinical efficacy) at defined time-points will be permanently discontinued. This design allows for collection of long-term safety data and avoids continued treatment of those subjects who do not respond to study medication.

From January 2017, all subjects who are at Week 72 or beyond will receive once-daily tablet formulation (15 mg QD or 30 mg QD). Preliminary results of a bioequivalent study demonstrated that single 15 mg and 30 mg doses of the once-daily formulation provide comparable AUC, but significantly lower  $C_{max}$  than single doses of 12 mg immediate release (IR) formulation (equivalent to 6 mg BID dose) and 24 mg IR formulation (equivalent to 12 mg BID dose), respectively. At steady-state, the once-daily dose of 15 mg QD is predicted to achieve comparable daily AUC, lower or comparable  $C_{max}$ , and comparable  $C_{trough}$  to 6 mg BID IR formulation, and the once-daily dose of 30 mg QD is predicted to be equivalent to 12 mg BID IR.

Subjects who are on 6 mg BID (IR) capsule dosing will be transitioned to 15 mg QD tablet dosing. Subjects who are on 12 mg BID dosing will be transitioned to 30 mg QD dosing. Capsule formulation will not be available to the subjects after transition to tablet formulation.

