## **8.1.5 Efficacy Analysis**

### **8.1.5.1 Efficacy Variables**

The efficacy endpoints of this study include the ACR20/50/70 response rates at Weeks 6, 12, 24, 36, 48, 60, 72, 84, 96 and every 24 weeks thereafter until the end of the study.

A subject will be considered an ACR20/50/70 responder if:

1. The counts for both SJC and TJC have reduced from Baseline by 20/50/70% or more; and
2. At least three of the five remaining ACR core set measures show reduction of 20/50/70% or more in baseline assessment:
  - Patient's Assessment of Pain (VAS),

- Patient's Global Assessment of Disease Activity,
- Physician's Global Assessment of Disease Activity,
- Patient's Assessment of Physical Function by Health Assessment Questionnaire – Disability Index (HAQ-DI),
- hsCRP.

Other efficacy endpoints of this study are:

- Individual components of ACR at every scheduled study visit (Weeks 6, 12, 24, 36, 48, 60, 72, 84, 96 and every 24 weeks thereafter until end of the study):
  - TJC
  - SJC
  - Patient's Global Assessment of Disease Activity
  - Physician's Global Assessment of Disease Activity
  - Patient's Assessment of Pain
  - hsCRP
  - Health Assessment Questionnaire Disability Index (HAQ-DI)
- Proportion of subjects achieving low disease activity (LDA) or clinical remission (CR) based on DAS28 [CRP] or CDAI criteria respectively at Weeks 6, 12, 24, 36, 48, 60, 72, 84, 96 and every 24 weeks thereafter until the end of the study.
- Proportion of subjects achieving CR at Weeks 6, 12, 24, 36, 48, 60, 72, 84, 96 and every 24 weeks thereafter until the end of the study.
- Change from Baseline in DAS28 [CRP] at Weeks 6, 12, 24, 36, 48, 72, 96 and every 24 weeks thereafter until the end of the study.
- Change from Baseline in CDAI at Weeks 6, 12, 24, 36, 48, 72, 96 and every 24 weeks thereafter until the end of the study.
- Change from Baseline in Patient Reported Outcomes at Weeks 6, 12, 24, 36, 48, 72, 96 and every 24 weeks thereafter until the end of the study:
  - FACIT – Fatigue Scale,

- Work Instability Scale for RA (RA-WIS),
- EuroQoL-5D (EQ-5D).

The proportion of subjects achieving Low Disease Activity (LDA) or Clinical Remission (CR), and the proportion of subjects achieving CR will be evaluated at Weeks 6, 12, 24, 36, 48, 60, 72, 84, 96 and every 24 weeks thereafter until the end of the study. The criteria will be based on DAS28 [CRP] or CDAI as follows:

	DAS28 [CRP]	CDAI
LDA	$2.6 \leq \text{to} < 3.2$	$2.8 < \text{to} \leq 10$
CR	$< 2.6$	$\leq 2.8$

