9.1.1 Definition of Missing Data Imputation

As Observed (AO)

The AO analysis will not impute values for missing evaluations. All observed data will be used in the analysis. The AO analysis will be applied to long-term efficacy analysis.

Mixed Model Repeated Measures (MMRM) and Generalized Linear Mixed Model (GLMM)

The repeated measure analysis will be conducted using mixed model including As Observed measurements at all visits. MMRM will be used for continuous endpoints and GLMM will be used for binary endpoints. The mixed models will include the categorical fixed effects of treatment, visit and treatment-by-visit interaction. Prior RCT study will also be included as a fixed factor in the model. For the MMRM analysis of change from baseline in continuous endpoints, the baseline measurement will be included as a continuous fixed covariate. The categorical fixed effect of subject's discontinuation status may also be included in the model as appropriate. Unstructured, Toeplitz, compound symmetry, or other covariance structures may be considered.

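### Long-term As Observed ACR20 leaves out subjects removed for failing ACR20's own joint criterion, so it is biased upward, and no planned analysis counts those removals as non-response

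*SAP*

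**What the plan says.** **Removal rule.** Protocol 5.1 has three routes out. A subject raised to 12 mg BID at Week 6 is discontinued if the joint criterion is still missed at Week 12. A subject raised at Week 12 leaves if they "fail to achieve at least 20% improvement from RCT Baseline in both TJC and SJC with 12 mg BID at Week 18". After Week 12, discontinuation follows "if a subject fails to show at least 20% improvement from RCT Baseline in both TJC and SJC at 2 consecutive scheduled study visits". Protocol 5.4.1 lists the same failure among the withdrawal criteria: "Subject has failed to achieve at least 20% improvement from Baseline (RCT period) in TJC and SJC with upadacitinib". Protocol 5.6 gives the purpose, which is to avoid continued treatment of non-responders: subjects "unable to achieve at least 20% improvement in both SJC and TJC (minimum clinical efficacy) at defined time-points will be permanently discontinued".

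**Endpoint.** Protocol 8.1.5.1 makes the first ACR condition "The counts for both SJC and TJC have reduced from Baseline by 20/50/70% or more; and" and then asks for three of the five other components. SAP 9.4.1 has the same structure. SAP 5.2 sets baseline before the first RCT dose, which is also the reference for the removal rule.

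**Missing data.** SAP 9.1 bases all efficacy summaries on As Observed (AO) data, and SAP 9.1.1 says "The AO analysis will not impute values for missing evaluations". Protocol 8.1.5.2 is likewise observed cases only. SAP 9.2 and Table 2 add a GLMM for binary endpoints in treatment sequences 1 and 2, fitted to the same data. Discontinuation status is an optional model term. Lack-of-efficacy discontinuations are tabulated in disposition (SAP 7.0), not in efficacy.

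**The concern.** The rule that decides who stays and the endpoint measured in those who stay share a threshold and a baseline. Protocol 5.1 can be read as failing either count or failing both. On either reading, a subject who meets the rule is an ACR20 non-responder at that visit, and so an ACR50 and ACR70 non-responder too. Once that subject has left, the later AO rate is computed without them.

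The objective in Protocol 4.0 and SAP 4.1 includes long-term efficacy. A flat or rising curve to Week 312 would naturally be read as durable response, although the removal rule alone can produce that shape. The complementary figure, the share of all treated subjects still on drug and responding, is not a planned display.

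**Working it through.** **No stated figure to reproduce.** The main study gives no expected ACR20 rate, removal rate or sample size calculation. Protocol 8.2 only anticipates up to 500 subjects; SAP 4.2 reports 494 enrolled. Every percentage below therefore rests on an assumption.

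**Step 1: direction.** Let N be subjects treated, d subjects removed by the rule, and r responders still in the study, with no other dropout.

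- AO rate = r/(N − d)
- Rate with removed subjects as failures = r/N = AO × (1 − d/N)
- Gap = AO × d/N, never negative

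**Step 2: size of the gap.** Take N = 494, assuming all enrolled subjects were treated. The half-width is 1.96 × √[AO(1 − AO)/(N − d)].

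| Removed | AO 70%: failures counted (gap; half-width) | AO 80% | AO 90% |
|---|---|---|---|
| 5% | 66.5% (3.5; 4.1) | 76.0% (4.0; 3.6) | 85.5% (4.5; 2.7) |
| 10% | 63.0% (7.0; 4.3) | 72.0% (8.0; 3.7) | 81.0% (9.0; 2.8) |
| 20% | 56.0% (14.0; 4.5) | 64.0% (16.0; 3.9) | 72.0% (18.0; 3.0) |
| 40% | 42.0% (28.0; 5.2) | 48.0% (32.0; 4.6) | 54.0% (36.0; 3.4) |

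From 10% removed upward, the gap exceeds the half-width of the AO confidence interval in every cell.

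**Step 3: shape over time.** Simulation of 100,000 subjects with up-titration at Weeks 6 and 12, re-assessment at Weeks 12 and 18, then removal at two consecutive joint failures (a Week 12 failure may count as the first). There is no other dropout. Assumed latent scores: joint mean 1.0, other components mean 0.8, between-subject SD 1.5, correlation 0.7, visit SD 1.0, response above zero.

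| Scenario | True rate, Wk 6 → 312 | AO Wk 12 | AO Wk 24 | AO Wk 96 | AO Wk 312 | Removed = failure, Wk 312 | Still in, Wk 312 |
|---|---|---|---|---|---|---|---|
| Flat | 53.9 → 54.1% | 54.1% | 65.8% | 73.3% | 79.8% | 40.5% | 50.7% |
| Flat, with gain of 0.5 on up-titration | 54.3 → 59.7% | 58.0% | 67.4% | 73.8% | 79.6% | 44.4% | 55.8% |
| Slow loss | 54.3 → 30.2% | 53.3% | 64.1% | 67.0% | 61.7% | 22.5% | 36.5% |
| Fast loss | 54.3 → 7.0% | 51.8% | 61.3% | 57.1% | 33.8% | 4.8% | 14.1% |

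The identity holds in the first row: 79.8% × 50.7% = 40.5%.

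**Step 4: a second set of assumptions.** Mean joint improvement 45–55%, between-subject SD 30 points, visit SD 18 points, 8% of joint responders failing the three-of-five part. Only the two-consecutive-visit rule acts; up-titration and the Week 12/18 removals are left out. With a flat true rate of 64–73%, AO at Week 312 is about 88%, and counting rule-removed subjects as failures gives 46–58%. A different choice for the correlation between the two joint counts gives a true rate of 60–70%, AO 87–88% and 42–54%.

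**Step 5: the GLMM.** A random-intercept logistic model with visit effects, fitted to pooled data of the Step 4 kind, gave Week 312 marginal rates of 62–65% where the truth was 60%, and 75% where it was 70%, against AO of 87–88%. It removes most of the spurious rise, because a removed subject's failing visits stay in the likelihood. It does not set later visits to failure.

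**The case against.** **The GLMM already answers it.** In part. Removal acts on recorded joint counts, so it depends largely on observed data, which is what MAR needs, and Step 5 supports this. Estimating response as if subjects had stayed is a different estimand, not an error. Three limits remain. The model covers sequences 1 and 2 only. Those groups are formed after baseline: joint failures at Weeks 6 and 12 should be up-titrated out of sequence 1, which enriches it further. And SAP Appendix D argues MAR only for COVID-19 missingness, not for removal on efficacy.

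**Stronger readings a reader might infer, which the documents do not support:**

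- *The AO curve must rise by design.* It need not. Under fast loss it falls to 33.8%, though it still overstates the true 7.0%.
- *Removed subjects are ignored altogether.* They drop out only after removal. Earlier failing visits count as non-response (SAP 9.4.1, examples B and C), and a Premature Discontinuation visit collects joint counts and can fall in an analysis window.
- *The share of all treated cannot be known.* A reader could add responder counts over the three sequences and divide by the number treated. The SAP simply does not present it.
- *Only 24–40% would be responding at Week 312.* That range arises under the Step 4 assumptions only if 6–10% a year of assumed random dropout is also counted as failure. It is not the effect of the removal rule.
- *An intended analysis was dropped, because Protocol 1.3 lists* "Non Responder Imputation". An abbreviation list is not evidence of that.

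**Other points that stand.** LDA and CR use thresholds other than the removal rule, so their bias is less direct and was not simulated. Changes to background therapy are allowed after Week 24, so flat-response scenarios may overstate removal. Protocol 5.3.3 gives a different baseline, before active upadacitinib; under it the two criteria would not coincide exactly for RCT placebo subjects. The study is descriptive, without tests, and Protocol 5.6 stresses safety and tolerability.

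**Conclusion.** The point holds as a bias in interpretation. AO rates at later visits are selected on the joint part of the endpoint, and no planned efficacy analysis counts a removed subject as a failure afterwards. The direction follows from the identity in Step 1; the size is not calculable from the documents. With no true change over time and no other dropout, the two sets of assumptions together give AO of about 80–88% at Week 312 against a true 54–73%, and about 41–58% when only rule-removed subjects count as failures. These figures show what the rule can do and do not forecast this trial. Because the analyses are descriptive, the remedy is a supportive display rather than a new main analysis; but the AO curve alone should not be read as evidence of sustained response in all treated subjects.

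**What to change.** Keep AO and the GLMM, and leave the clinical stopping rule as it is. In SAP 9.1.1, 9.2 and Table 2, add supportive tables of ACR20/50/70, LDA and CR, overall and by treatment sequence:

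- **(a)** Subjects who discontinued for lack of efficacy or adverse event are non-responders at all later visits. Subjects missing for other reasons (withdrawn consent, lost to follow-up, non-compliance, other, COVID-19 logistics) are left out of the denominator at that visit.
- **(b)** As a lower bound, the denominator is all treated subjects and discontinuation for any reason is non-response, with COVID-19 logistical missingness shown separately.

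SAP 7.0 also lists COVID-19 infection and need for alternative or prohibited therapy as reasons. Version (a) should assign both in advance. Beside each AO rate, print the number observed and the number removed for lack of efficacy.

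The cost is SAP wording and one more set of tables; discontinuation reasons are already on the CRF, so no new data are needed. Version (b) is conservative for administrative dropout and should be labelled as a bound.

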9.2 Long-Term Efficacy Analysis

Assessments to evaluate long-term efficacy will be analyzed for the following measures at Weeks 6, 12, 24, 36, 48, 60, 72, 84, 96 and every 12 weeks until Week 312.

- ACR20/50/70 response rates;
- Change from baseline in individual ACR components;
- Change from baseline in DAS28 (CRP);
- Change from baseline in CDAI and SDAI;
- Proportion of subjects achieving LDA and proportion of subjects achieving CR based on DAS28 (CRP), CDAI and SDAI criteria;
- Change from baseline in Patient Reported Outcomes, including FACIT-Fatigue Scale, RA-WIS, and EQ-5D;

Analyses will be based on As Observed (AO) data. Descriptive statistics will be provided for each treatment group sequence in the Open-Label Treated Population as defined in Section 9.1. These include the number of observations, mean, standard deviation, and 95% CI for continuous endpoints; and frequencies and percentages with 95% CI using normal approximation for binary endpoints. In addition, longitudinal analysis will be

performed using MMRM or GLMM as described in Section 9.1.1 for all endpoints for treatment sequences 1 and 2. Point estimates and 95% CI from the model will be provided. Plots over time will be provided.

Table 1 below provides the overview of the long-term efficacy analysis to be performed on different endpoints.

Table 2. Summary of Long-Term Efficacy Analysis

Measure of Interest	Analysis Method
Binary endpoints: 
 • ACR20 at each visit • ACR50 at each visit • ACR70 at each visit • LDA based on DAS28 (CRP) at each visit • LDA based on CDAI and SDAI at each visit • CR based on DAS28 (CRP) at each visit • CR based on CDAI and SDAI at each visit 	
 • Point estimate and 95% CI of the response rate for each treatment sequence • Point estimate and 95% CI of the response rate using GLMM model for treatment sequences 1 and 2 • Plots over time (for ACR responses and LDA/CR based on DAS28 and CDAI) • Imputation: AO • Population: open-label treated population
Continuous endpoints: 
 • Change from baseline for DAS28 (CRP) at each visit • Change from baseline for CDAI and SDAI at each visit • Change from baseline for each ACR individual component (i.e., TJC, SJC, Physician's Global Assessment of Disease Activity, Patient's Global Assessment of Disease Activity, Patient's Assessment of Pain, HAQ-DI, hsCRP) at each visit • Change from baseline for other PROs (FACIT, RA-WIS, EQ-5D) at each visit 	
 • Point estimate and 95% CI of mean change from baseline for each treatment sequence together with SD • Point estimate and 95% CI of change from baseline using MMRM model for treatment sequences 1 and 2 • Plots over time (for DAS28 (CRP), CDAI and SDAI) • Imputation: AO • Population: open-label treated population

